3.7.3 Off Study Procedure

Authorized staff must notify Central Registration Office (CRO) when a subject is taken off-study. An off-study form from the web site (<http://home.ccr.cancer.gov/intra/eligibility/welcome.htm>) main page must be completed and faxed to [contact].

4 CONCOMITANT MEDICATIONS AND SUPPORTIVE MEASURES

4.1 MANAGEMENT OF BLEEDING, HEMATOLOGIC AND BLOOD PRODUCT SUPPORT

Blood product support should be provided to maintain platelets $\geq 25,000$ cells/mcl and as clinically indicated.

Growth factor support to patients who experience grade 4 neutropenia (ANC $<500/\mu\text{L}$) will not be administered prophylactically, but may be administered as defined in Section 3.3. In addition,

growth factor support may be administered to patients who develop grade 4 neutropenia if clinically indicated, for example in patients who develop sepsis.

If patients experience any signs of bleeding (\leq Grade 2) including, epistaxis, hematuria, hematemesis or blood in the stool, the patient will immediately undergo a comprehensive clinical evaluation, coagulation profile including PT/PTT/fibrinogen, thrombin time, PFA-100, D-dimer, and comprehensive metabolic panel including Ca^{2+} and ionized calcium. Any abnormality will be corrected as clinically indicated with blood product support with guidance by hematology (NIH CC hematology consult). If a patient experiences bleeding in the setting of a normal platelet count, platelet function tests will be performed and the patient should be transfused with platelets even in the presence of a normal platelet count while these studies are pending. Mithramycin has also been known to block SP1, and SP1 has been shown to play a role in the expression of GPIIb. Therefore, mithramycin may cause a deficiency in this protein in mature platelets theoretically mimicking the bleeding diathesis, Glanzmanns thrombasthenia (45).

4.2 ANTIEMETIC THERAPY

Ondansetron (or other drugs from this same class of anti-emetics, as per investigator preference) prior to and after mithramycin as needed. Additional antiemetic therapy may be provided by either intravenous or oral route as needed. Patients that experience significant nausea during cycle one may be offered aprepitant.

4.3 HEPATOTOXICITY PROPHYLAXIS USING DEXAMETHASONE

Patients will receive 2.5 mg dexamethasone/m² BSA PO or IV starting 12-16 hours before the first dose of mithramycin, then prior to the first dose of mithramycin and then twice daily until 24 hours after the last dose of mithramycin (46, 47).

4.4 ANTIDIARRHEALS

Antidiarrheal agents will be prescribed using standard clinical practice guidelines at the preference of the investigator.

4.5 ELECTROLYTE REPLACEMENT

Electrolyte replacement will be provided to maintain serum levels within normal limits.

4.6 QTc PROLONGATION

If grade 3 or 4 QTc prolongation is noted on a 12-lead EKG, then repeat the 12-lead EKG to confirm finding and consult cardiology. Hold next dose until cardiology consult is obtained.

5 CORRELATIVE STUDIES / BIOSPECIMEN COLLECTION

5.1 PHARMACOKINETIC (PK) SAMPLING

Detailed plasma pharmacokinetic (PK) sampling of mithramycin will be performed prior to and at the completion of the first dose of mithramycin during cycle 1 on the phase I and phase II portion of the trial. In addition, trough and end of infusion samples will be obtained with the day 2, 4 and 7 doses to assess mithramycin accumulation, and samples will be obtained 24 and 48 hours after the day 7 dose of mithramycin on days 8 and 9, respectively. Deviations in the timing of the PK samples will be recorded on the PK worksheets, but not reported as a protocol deviation. In addition, the omission of individual PK samples will be recorded, but not be reported as deviation

to the NCI IRB. PK analysis will be performed at the NCI, POB, PETS. Refer to details in **Appendix 4: Pharmacokinetic Worksheet for Mithramycin (Phase I and Phase II) For nursing staff** and **Appendix 5: Pharmacokinetic Worksheet for Mithramycin (Phase I and Phase II) For Laboratory Personnel and Research Nurses.**

5.2 STUDIES ON TUMOR TISSUE

5.2.1 Evaluation of NR0B1 expression on archival tumor tissue

In all patients with Ewing sarcoma and archival tumor tissue available, evaluation of NR0B1 as target of mithramycin will be evaluated using immunohistochemistry in the Laboratory of Pathology by [name] and [name] (See **Appendix 7: Studies to be performed on tumor tissue** for details).

5.2.2 Confirmation of EWS/FLI1 fusion transcript for eligibility for phase II portion:

Presence of the EWS-FLI1 fusion transcript will be determined during histologic confirmation of disease with a CLIA approved EWS-FLI1 paraffin assay in the Laboratory of Pathology CCR, NCI, unless a pathology report documenting presence of the transcript using a CLIA approved assay is obtained from the referring institution (See **Appendix 7: Studies to be performed on tumor tissue for details**). If archival tumor tissue is not available in paraffin blocks, 5 consecutive unstained slides and an H& E slide may be used.

5.2.3 Evaluation of NR0B1 expression from mandatory tumor biopsies

In patients with Ewing sarcoma and EWS-FLI1 fusion transcript ≥ 18 years old, who have disease amenable to percutaneous biopsy, and who meet other eligibility criteria for biopsy, a biopsy will be obtained prior to treatment and at steady state on treatment. Patients who meet these criteria will have to agree to the biopsies in order to be able to participate in the trial.

Tissue will be collected and immediately sectioned, a portion will be separated and frozen on dry ice for RNA collection for microarray and/or gene signature evaluation of EWS-FLI1 downstream target expression (see Section 5.2.3.1). Another portion will be imbedded in paraffin and sectioned. This tissue will be stained using immunohistochemistry for NR0B1 and if tissue remains, proteins in the apoptotic pathway will be evaluated including survivin (BIRC5), XIAP, Caspase-8 (CASP8), and BCL-XL (BCL2L1) (See **Appendix 7: Studies to be performed on tumor tissue** for details).

5.2.4 Other Investigations (See **Appendix 7: Studies to be performed on tumor tissue)**

5.2.4.1 RNA for EWS-FLI1 gene signature

When remaining tissue is available from tumor biopsies pre treatment and at steady state, EWS-FLI1 gene signature analysis will be performed on the fluidigm platform.

5.2.4.2 Microarray expression profiling

When tissue is available, microarray expression profiling using standard Affymetrix HU.133 platform.

5.2.4.3 Establishment of Cell Lines

Finally, if adequate tissue is available and participants agree, efforts will be made to establish cell lines.

5.2.5 Future Research Studies

5.2.5.1 Serum samples for potential biomarker analysis: One serum sample will be obtained prior to cycle 1, and then at **the** same time of restaging studies after every even cycle. Details regarding sample handling and time points are provided in [**Appendix 6: Serum Sample For Potential Biomarker \(Phase I and Phase II\).**](#)

5.3 SAMPLE STORAGE, TRACKING AND DISPOSITION

5.3.1 Pediatric Research Samples: *Blood Drawing Limits for Research Purposes*

Research blood sample aliquot size will be minimized for patients < 18 years of age and the total amount restricted to a maximum of 3 ml/kg per draw and 7 ml/kg per 6-week period (maximum 450 ml). If the volume of blood needed for research samples exceeds the sample limits described here, pharmacokinetic samples have priority over the serum samples for future biomarker analysis.

5.3.2 NIH Policy on Research Use of Stored Human Samples, Specimens, or Data

This study is coordinated by the Pediatric Oncology Branch, NCI. Sample collection and initial processing will be conducted as outlined in Appendices 4 through 8. Samples will only be labeled with study identification numbers; no personally identifiable information should be included.

Storage of pharmacokinetic and pharmacodynamic samples will occur in designated monitored freezers (-80°C) in the Pharmacology & Experimental Therapeutics Section (PETS) Laboratory, POB, NCI on 1 West. Imaging studies will be stored at the PETS laboratory on password protected computers. All samples obtained on this study will be tracked using LabMatrix. Pharmacokinetic samples will be analyzed at the NCI PETS. Samples will be identified and tracked using unique identifiers linked to each subject's unique patient number (study number). Codes linking personal identifiable information to the unique identifier will be stored in secure, computer servers with limited coded access or locked file cabinets in POB with access limited to the PI or study coordinator. Archival tumor tissue (blocks or unstained slides will be stained for NR0B1 and other markers at the Laboratory of Pathology by [name]. Unused material will be returned to the submitting institution upon their request. Mandatory tumor samples will be analyzed for NR0B1 expression at the Laboratory of Pathology. Gene expression signatures will be analyzed in [name] laboratory. Samples will be stored at -80°C in the laboratory of [name]. Samples will be tracked and considered the responsibility of the principal investigator. The study will remain open and status reported to the NCI IRB until all samples have been analyzed, reported or destroyed. Unintentional loss or destruction of any samples will be reported to the NCI IRB as part of annual continuing reviews. Any use of samples not outlined in Section **5** will require prospective NCI IRB review and approval.

At the termination of this protocol, if additional studies are to be performed on any samples retaining patient identifiers, obtained during the conduct of this trial, a Request to Conduct Research for Stored Human Samples Specimens, or Data Collected in a Terminated NCI-IRB Protocol will be submitted. Otherwise, specimens will be disposed of in accordance with the environmental protection laws, regulations and guidelines of the Federal Government and the State of Maryland.

6 DATA COLLECTION AND EVALUATION

6.1 DATA COLLECTION

The PI will be responsible for overseeing entry of data into an in-house password protected electronic system and ensuring data accuracy, consistency and timeliness. The principal investigator, associate investigators/research nurses and/or a contracted data manager will assist with the data management efforts. All data obtained during the conduct of the protocol will be kept in secure network drives or in approved alternative sites that comply with NIH security standards. Primary and final analyzed data will have identifiers so that research data can be attributed to an individual human subject participant.

End of study procedures: Data will be stored according to HHS, FDA regulations, and NIH Intramural Records Retention Schedule as applicable.

Loss or destruction of data: Should we become aware that a major breech in our plan to protect subject confidentiality and trial data has occurred, the IRB will be notified.

Patients will complete a patient log for reactions and symptoms related to mithramycin infusion ([Appendix 10: Patient Log for Reactions/Symptoms](#)), and a concomitant medication log ([Appendix 11: Patient Log for Concomitant Medication](#)). Physicians or care providers, who perform on study evaluations between cycles will receive instructions regarding required on study evaluations ([Appendix 12: Monitoring Toxicities Between Mithramycin Cycles with Local Physician](#)).

6.1.1 Source Documents

Source documents are original documents, data and records which include hospital records, clinic and office charts, laboratory data/information, patient diaries or evaluation checklists, pharmacy dispensing and other records, recorded data from automated instruments, microfiches, photographic negatives, microfilm or magnetic media, x-rays. The Principal Investigator will permit trial-related monitoring, audits, IRB review, and regulatory inspections, providing direct access to source data documents.

6.2 RESPONSE CRITERIA

Objective response and progression will be evaluated in this study using the new international criteria proposed by the Response Evaluation Criteria in Solid Tumors (RECIST) Committee [version 1.1 (48)].

Note: Lesions are either measurable or non-measurable using the criteria provided below. The term “evaluable” in reference to measurability will not be used because it does not provide additional meaning or accuracy.

6.2.1 Response Criteria for Radiographic Studies

6.2.1.1 Measuring of Soft Tissue Disease

Response and progression will be evaluated in this study using the new international criteria proposed by the revised Response Evaluation Criteria in Solid Tumors (RECIST) guideline [version 1.1 (48)]. Changes in the largest diameter (unidimensional measurement) of the tumor lesions and the shortest diameter in the case of malignant lymph nodes are used in the RECIST criteria.

a. Evaluation of Target Lesions

Complete Response (CR)

Disappearance of all target lesions. Any pathological lymph nodes (whether target or non-target) must have reduction in short axis to <10 mm

Partial Response (PR)

At least a 30% decrease in the sum of the diameters of target lesions, taking as reference the baseline sum diameters

Progressive Disease (PD)

At least a 20% increase in the sum of the diameters of target lesions, taking as reference the smallest sum on study (this includes the baseline sum if that is the smallest on study). In addition to the relative increase of 20%, the sum must also demonstrate an absolute increase of at least 5 mm. (Note: the appearance of one or more new lesions is also considered progressions)

Stable Disease (SD)

Neither sufficient shrinkage to qualify for PR nor sufficient increase to qualify for PD, taking as reference the smallest sum diameters while on study

b. Evaluation of Non-Target Lesions

Complete Response (CR)

Disappearance of all non-target lesions and normalization of tumor marker level. All lymph nodes must be non-pathological in size (<10 mm short axis)

Note: If tumor markers are initially above the upper normal limit, they must normalize for a patient to be considered in complete clinical response.

Non-CR/Non-PD (Stable Disease, SD)

Persistence of one or more non-target lesion(s) and/or maintenance of tumor marker level above the normal limits.

Progressive Disease (PD)

Appearance of one or more new lesions and/or *unequivocal progression* of existing non-target lesions. *Unequivocal progression* should not normally trump target lesion status. It must be representative of overall disease status change, not a single lesion increase.

Although a clear progression of “non-target” lesions only is exceptional, the opinion of the treating physician should prevail in such circumstances, and the progression status should be confirmed at a later time by the review panel (or Principal Investigator).

c. Evaluation of Best Overall Response

The best overall response is the best response recorded from the start of the treatment until disease progression/recurrence (taking as reference for progressive disease the smallest measurements recorded since the treatment started). The patient's best

response assignment will depend on the achievement of both measurement and confirmation criteria.

Target Lesions	Non-Target Lesions	New Lesions	Overall Response	Best Overall Response when Confirmation is Required*
CR	CR	No	CR	≥ 4 wks. Confirmation**
CR	Non-CR Non-PD	No	PR	≥ 4 wks. Confirmation**
CR	Not evaluated	No	PR	
PR	Non-CR Non-PD Not evaluated	No	PR	
SD	Non-CR Non-PD Not evaluated	No	SD	Documented at least once ≥ 4 wks. from baseline**
PD	Any	Yes or No	PD	No prior SD, PR or CR
Any	PD***	Yes or No	PD	
Any	Any	Yes	PD	

*See RECIST 1.1 manuscript for further details on what is evidence of a new lesion.
**Only for non-randomized trials with response as primary endpoint.
***In exceptional circumstances, unequivocal progression in non-target lesions may be accepted as disease progression

- d. Patients with a global deterioration of health status requiring discontinuation of treatment without objective evidence of disease progression at that time should be reported as “*symptomatic deterioration*.” Every effort should be made to document the objective progression even after discontinuation of treatment.
- e. In some circumstances, it may be difficult to distinguish residual disease from normal tissue. When the evaluation of complete response depends on this determination, it is recommended that the residual lesions be investigated (fine needle aspirate/biopsy) before confirming the complete response status.

6.2.2 Confirmatory Measurement/Duration of Response

a. Confirmation

To be assigned a status of PR or CR, changes in tumor measurements must be confirmed by repeat assessments that should be performed at least 4 weeks after the criteria for response are first met. Objective response measures will be confirmed at the Coordinating Center. The participating site should forward staging studies of participants who have achieved PR or CR status to the Coordinating Center for confirmation.

b. Duration of Overall Response

The duration of overall response is measured from the time measurement criteria are met for CR or PR (whichever is first recorded) until the first date that recurrent or

progressive disease is objectively documented (taking as reference for progressive disease the smallest measurements recorded since the treatment started).

The duration of overall CR is measured from the time measurement criteria are first met for CR until the first date that progressive disease is objectively documented.

6.2.3 Measurable Disease

Measurable lesions are defined as those that can be accurately measured in at least one dimension (longest diameter to be recorded) as ≥ 20 mm by chest x-ray, as ≥ 10 mm with CT scan, or ≥ 10 mm with calipers by clinical exam. All tumor measurements must be recorded in millimeters (or decimal fractions of centimeters).

Note: Tumor lesions that are situated in a previously irradiated area might or might not be considered measurable. *If the investigator thinks it appropriate to include them, the conditions under which such lesions should be considered must be defined in the protocol.*

6.2.4 Malignant Lymph Nodes

To be considered pathologically enlarged and measurable, a lymph node must be ≥ 20 mm in short axis when assessed by CT scan (CT scan slice thickness recommended to be no greater than 5 mm). At baseline and in follow-up, only the short axis will be measured and followed.

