2 ELIGIBILITY ASSESSMENT AND ENROLLMENT

2.1 ELIGIBILITY CRITERIA

2.1.1 Inclusion Criteria

2.1.1.1 Diagnosis

Patient's current disease state must be one for which there is no known curative therapy or therapy proven to prolong survival with an acceptable quality of life.

Phase I Portion: Measurable or evaluable refractory or recurrent extracranial solid tumors, excluding brain tumors and cerebral metastases.

Phase II Portion adults and children: Refractory or recurrent extracranial Ewing sarcoma with EWS-FLI1 fusion transcript. Patients enrolled to this cohort must have measurable disease. Presence of the transcript will be determined during histologic confirmation of disease with a CLIA approved EWS-FLI paraffin assay in the Laboratory of Pathology CCR, NCI, unless a pathology report documenting presence of the transcript using a CLIA approved assay is obtained from the referring institution.

2.1.1.2 Histologic confirmation of disease in the Laboratory of Pathology, CCR, NCI, NIH.

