6.2.5 Non-Measurable Disease

All other lesions (or sites of disease), including small lesions (longest diameter <10 mm or pathological lymph nodes with ≥ 10 to <15 mm short axis), are considered non-measurable disease. Bone lesions, leptomeningeal disease, ascites, pleural/pericardial effusions, lymphangitis cutis/pulmonitis, inflammatory breast disease, and abdominal masses (not followed by CT or MRI), are considered as non-measurable.

Note: Cystic lesions that meet the criteria for radiographically defined simple cysts should not be considered as malignant lesions (neither measurable nor non-measurable) since they are, by definition, simple cysts.

‘Cystic lesions’ thought to represent cystic metastases can be considered as measurable lesions, if they meet the definition of measurability described above. However, if non-cystic lesions are present in the same patient, these are preferred for selection as target lesions.

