6.2.6 Target Lesions

All measurable lesions up to a maximum of 2 lesions per organ and 5 lesions in total, representative of all involved organs, should be identified as **target lesions** and recorded and measured at baseline. Target lesions should be selected on the basis of their size (lesions with the longest diameter), be representative of all involved organs, but in addition should be those that lend themselves to reproducible repeated measurements. It may be the case that, on occasion, the largest lesion does not lend itself to reproducible measurement in which circumstance the next largest lesion which can be measured reproducibly should be selected. A sum of the diameters (longest for non-nodal lesions, short axis for nodal lesions) for all target lesions will be calculated and reported as the baseline sum diameters. If lymph nodes are to be included in the sum, then only the short axis is added into the sum. The baseline sum diameters will be used as reference to further characterize any objective tumor regression in the measurable dimension of the disease.

Progressive disease by RECIST criteria [1] noted after the first re-staging scan may represent disease that was not detected on the pre-study scan, and a confirmatory scan will be required at the next scheduled re-staging evaluation unless clinically not indicated. If confirmed, progression should be dated by the initial time when the lesions are first detected. If progressive disease by RECIST criteria is seen after cycle 2, but not confirmed on subsequent restaging scan, the scans from after cycle 2 would serve as the baseline scan to evaluate for disease progression (49).

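### Sections 6.2.4 and 6.2.5 give lymph-node limits that do not meet (20 mm and 15 mm short axis), so nodes of 15 to under 20 mm are open to inconsistent classification

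*Combined protocol and SAP*

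**What the plan says.** Section 6.2 adopts RECIST version 1.1 (reference 48) and then writes out its own measurement rules.

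- Section 6.2.3 sets the general limit for a measurable lesion by longest diameter: "as ≥ 10 mm with CT scan, or ≥ 10 mm with calipers by clinical exam".
- Section 6.2.4 gives the node-specific CT rule: "a lymph node must be ≥ 20 mm in short axis when assessed by CT scan".
- Section 6.2.5 defines non-measurable disease. It opens "All other lesions (or sites of disease), including small lesions" and, among the examples, names "pathological lymph nodes with ≥ 10 to <15 mm short axis".
- Section 6.2.6 draws target lesions from measurable disease: "All measurable lesions up to a maximum of 2 lesions per organ and 5 lesions in total". On nodes it adds: "If lymph nodes are to be included in the sum, then only the short axis is added into the sum".
- Section 6.2.1.1 has a node condition for CR: "Any pathological lymph nodes (whether target or non-target) must have reduction in short axis to <10 mm".
- Section 2.1.1.1 says of phase II: "Patients enrolled to this cohort must have measurable disease".

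Section 8.2 makes objective response by RECIST 1.1 the phase II primary endpoint. It is judged by a two-stage rule: stop if 0 of 9 respond; otherwise enter 15 more and require 3 or more responses in 24.

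**The concern.** Adjacent sections that define measurable and non-measurable nodes should share a boundary. Here measurable starts at 20 mm, while the node range named as non-measurable ends at 15 mm. The sections also differ on which nodes are pathological: 6.2.4 ties that description to the 20 mm floor, whereas 6.2.5 applies it to nodes of 10 to under 15 mm.

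A reader who relies on 6.2.4 would make a 17 mm node a non-target lesion. Under 6.2.7 it then need not be measured, and its shrinkage adds nothing towards a PR. A reader who takes the 15 mm bound in 6.2.5 as the start of measurability could select the same node as a target and put its short axis into the sum. What is at stake is consistent classification at entry, at baseline and at each response assessment in a small single-arm study.

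**Working it through.** **1. The two sections side by side, by short axis on CT**

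| Short axis | 6.2.4 | Node range named in 6.2.5 | Agreement |
|---|---|---|---|
| 10 to <15 mm | not measurable | named as non-measurable | yes |
| 15 to <20 mm | not measurable | outside the named range | limits do not meet |
| 20 mm or more | measurable | outside the named range | yes |

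The gap is 20 − 15 = 5 mm. Section 6.2.8 also accepts superficial lesions, palpable nodes included, from 10 mm by calipers. That is a different method of measurement and does not settle the CT band.

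**2. Does the catch-all settle it?** Read literally, yes: a node that fails 6.2.4 belongs to the other lesions of 6.2.5 and is non-measurable. But if measurability began at 20 mm, the natural upper end of the named node range would be 20 mm. The 15 mm bound does no work on that reading, which is why the text invites a second one.

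**3. Where classification matters**

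- *Eligibility.* Section 2.1.1.1 needs measurable disease. A non-nodal lesion of at least 10 mm on CT already satisfies 6.2.3, so status changes only if a node in the band is the sole candidate.
- *PR.* Section 6.2.1.1 requires a 30% fall in the baseline sum. Adding a node of *n* mm raises the required fall by 0.30 × *n*: 0.30 × 15 = 4.5 mm at the bottom of the band and just under 0.30 × 20 = 6.0 mm at the top. The node's own change then counts too, so the effect can go either way.
- *PD.* The same section requires a 20% rise over the smallest sum, and at least 5 mm. If baseline is the smallest sum, the node adds 0.20 × 15 = 3.0 mm to just under 0.20 × 20 = 4.0 mm to the 20% threshold.
- *CR.* The under-10 mm condition covers target and non-target nodes alike, and the non-target CR rule repeats it. CR therefore does not turn on target status.

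**4. The decision rule**, with b(*n*, *x*, *p*) the binomial probability of *x* responses in *n*:

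- Early stopping: (1 − *p*)^9. At *p* = 0.05, 0.95^9 = 0.630, which reproduces the stated 63%.
- Declared active: sum over *x* = 1 to 9 of b(9, *x*, *p*) × P(Bin(15, *p*) ≥ 3 − *x*). This gives 0.093 at *p* = 0.05 (limit 0.10) and 0.903 at *p* = 0.25 (target 0.90).

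The design reproduces and does not depend on the node limit. One reclassified patient can alter a decision only when the count sits at 0 versus 1 of 9, or 2 versus 3 of 24.

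**The case against.** The best defence is that there is only one floor. Section 6.2.4 is mandatory and is the only sentence that says when a node is measurable on CT; 6.2.5 is a catch-all with examples. No sentence says that a 15 to under 20 mm node is measurable. This stands to the extent that a reader might infer two rules giving opposite answers, and the documents do not support that: the second answer is only implied by the bound of an example. The mismatch remains, because the bound has no other use.

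There is also some protection in conduct. Section 3.1 describes a single institution, and 6.2.2 has PR and CR confirmed at the Coordinating Center. That should reduce reader-to-reader variation in responses. It does not cover eligibility, and it gives the confirming reader no threshold.

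A second tempting inference is a flip probability. The chance of continuing and ending with exactly 3 of 24 responses is b(24, 3, *p*) − b(9, 0, *p*) × b(15, 3, *p*): 0.058, 0.116 and 0.174 at true rates of 25%, 20% and 15%. The chance of exactly 1 of 9 is 0.225, 0.302 and 0.368. These are chances of sitting on a cut-off for any reason. To become chances of a changed verdict they would have to be combined with the chance that a patient's response status hangs on a node in the band, and the documents do not give that. They should not be read as the size of this problem.

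Finally, the documents cite the RECIST 1.1 guideline but nowhere state its node limit. They alone cannot prove that 15 mm is right; the internal support is the bound in 6.2.5.

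**Conclusion.** This is an internal inconsistency in an operative definition, and it should be corrected. It is confined to nodes of 15 to under 20 mm short axis on CT. It can change phase II eligibility only where such a node is the sole candidate measurable lesion; otherwise it can change target-lesion selection and the baseline sum behind PR and PD. The number of affected patients is not given, so no effect on the response rate, the error rates or the chance of a wrong decision can be stated.

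The conclusion assumes that the two figures are the intended text and not an artefact of PDF reading, of which there is no sign. It does not call the two-stage design into question, nor does it show that any patient has been misclassified.

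**What to change.** State one short-axis boundary for nodes on CT and use it in both 6.2.4 and 6.2.5, with the same meaning of pathological in each. Setting 6.2.4 to at least 15 mm meets the limit already in 6.2.5; check that figure against reference 48 before adopting it. If 20 mm is a deliberate choice, extend the 6.2.5 range to under 20 mm and say that the study departs from the limit 6.2.5 now uses and, if the check shows it, from the guideline.

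Say also how the single limit applies to patients already on study. Section 8.2 shows that at least two had entered phase II, at the earlier dose; they are assessed for response but not counted in the design. Baseline target-lesion selection should be re-checked for all enrolled patients with nodes in the band, and any change recorded.

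The cost is a short protocol amendment and a review of existing baseline scans. Sample size, decision rule, analysis method and treatment are unchanged.
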